4.2 Rationale for the Starting Dose and Dosing Schedule

The starting dose of this multiple doses study in human is determined according to the final result of the single dose study in healthy volunteers, the preliminary result of the multiple doses study in patients with lymphoma, as well as the result of the non-clinical toxicity studies.

In the HMPL-689 single dose escalation first-in-human study (CCI [REDACTED]), single dose of HMPL-689 30 mg was well tolerated with no DLT or SAE noted. The exposures of HMPL-689 measured by geometric mean AUC_{0-24h} values in human at dose levels of 1, 2.5, 5, 10, 20 and 30 mg were 39.9, 98.2, 195, 446, 877, and 1280 h•ng/mL, respectively. The geometric mean $t_{1/2}$ of HMPL-689 was around 7-9 hours.

In the multiple dose escalation study (CCI [REDACTED]), 2 DLTs were observed at 5 mg BID, and no DLT was observed at 2.5 mg BID or 5 mg QD. Re-challenging of 5 mg BID and evaluating of 10 mg QD were ongoing at the data cut-off date of 30 April 2018. The PK profile in Chinese patients with lymphoma on Day 1 was similar to that in male healthy volunteers in Australia with regard to $t_{1/2}$ and exposures (C_{max} and AUC) at the equivalent dose levels. After multiple oral doses for 15 days, the accumulation ratio was around 1-2. Partial responses were observed in all dose levels tested, including 2.5 mg BID, 5 mg BID and 5 mg QD.

In HMPL-689 4-week toxicity studies, the NOAEL were 0.5 mg/kg/day in dogs and 3 mg/kg/day in male rats, respectively. The AUC_{0-24h} was 754 h•ng/mL in male and 550 h•ng/mL in female for dogs, 1430 h•ng/mL in male rats for corresponded NOAELs, respectively.

According to total exposure of HMPL-689 in human and in preclinical toxicity studies, and the different protein binding rates of HMPL-689 in rat, dog and human, which was around 89.1%, 88.5% and 93.1%, respectively, the human equivalent dose of NOAEL, estimated by free exposure of HMPL-689, is likely to be 20-50 mg/day.

Based on the data above, HMPL-689 5 mg QD was selected as the initial dose in this study. A treatment cycle is defined as 28 days of continuous dosing.

4.3 Rationale for Selection of Patient Population

The clinical data have indicated that PI3K is abnormally activated in B-cell lymphomas. *In vitro* experiments have also demonstrated that PI3K molecule plays major role in activation and proliferation of B-NHLs, as previously discussed (Section 2.3). For example, down-regulation of PI3K was able to reduce proliferating signal as well as the expansion of DLBCL cells and spontaneous lymphoma cells from transgenic mice. These experiments indicate that hyperactivated PI3K or PTEN deletion plays important role in promoting activation of B-NHLs. Therefore, inhibition of PI3K activation in B-NHLs may block signal transduction, resulting in inhibition of B lymphoma cell proliferation or lead to induction of apoptosis in tumor cell. This approach may provide a powerful tool for treatment of B-cell lymphomas.

The patient population of Stage 1 (i.e., patients with relapsed, refractory or resistant lymphoma) has been selected because these patients have exhausted all approved therapeutic options available, and offered by standard of care. Based on previous clinical data of HMPL-689 in a similar population, HMPL-689 might be offered to these patients as an alternative therapeutic options. The inclusion criterion of Eastern Cooperative Oncology Group (ECOG) performance status of 0 or 1 has been selected to facilitate attribution of toxicities to disease or the introduction of this agent.

Patients with relapsed, refractory or resistant CLL/SLL, MCL, FL, MZL, PTCL, CBCL, and WM/LPL were selected for Stage 2 based on the preclinical and clinical data (Sections 2.2 and 2.3), which suggest that patients with these types of NHL are more likely to benefit from the treatment of PI3K δ inhibitor.

4.4 End of Study

The end of the study is defined as 18 months after the last patient has been enrolled in the study or all patients have discontinued the study treatment, whichever comes earlier.

5 MATERIALS AND METHODS

5.1 Patients

CCI

5.1.1 Inclusion Criteria

Patients must meet the following criteria to be eligible for study entry:

1. Signed Informed Consent Form (ICF);
2. Age ≥ 18 years;
3. Eastern Cooperative Oncology Group (ECOG) performance status of 0 or 1;
4. Histologically confirmed NHL of the following sub-types CLL/SLL, FL (grade 1-3a), MCL, MZL, LPL/WM, PTCL or CBCL;
 - Patients with CLL/SLL, FL (grade 1-3a), MCL and LPL/WM must have received at least 2 prior lines of systemic therapy.
 - Patients with MZL must have received at least 1 prior line of systemic therapy that includes an anti-CD20 monoclonal antibody agent.
 - Patients with PTCL and CBCL must have received at least 1 prior line of systemic therapy.
5. Patients with relapsed, refractory, or resistant NHL, as defined below:
 - Refractory to any prior regimen, defined as no response (complete response [CR] or partial response [PR]) to previous therapies, or progression within 6 months of completion of the last dose of prior therapy.
 - Those who can no longer tolerate/withstand cytotoxic chemotherapy and or available standard of treatment/care (SoT/SoC), where safety profile and risks of toxicity of other treatment options far outweigh any possible clinical benefit.
 - Those with no curative SoT or no reasonable access to available treatments, in particular, those who will benefit from this class of compound, in the opinion of the attending investigator.
6. In the dose expansion stage, patients must have measurable disease for objective response assessment, except for patients with CLL and WM/LPL

NOTE: measurable disease with FL, MCL, MZL, PTCL, CBCL or SLL defined as at least 1 bi-dimensionally measurable lesion (>1.5 cm in its largest dimension by computerized tomography [CT] scan), as defined in [Appendix 7](#)
7. Expected survival of more than 24 weeks as determined by principal investigator

8. Patients with prior treatment with any PI3K δ inhibitors are eligible for dose escalation. However, during dose expansion, only patients that discontinued PI3K δ inhibitor for reasons other than disease progression are eligible.
9. Male patients must use a condom and female patients of childbearing potential must agree to use highly effective contraceptive measures that result in a low failure rate (<1% per year) when used consistently and correctly, from the screening period, through the entire study period, and for 30 days after the last dose of study drug. These highly effective contraceptive measures, as defined by the Clinical Trials Facilitation Group (CTFG)*, include combined estrogen and progestogen hormonal contraception associated with inhibition of ovulation (oral, intravaginal, transdermal), progestogen-only hormonal contraception associated with inhibition of ovulation (oral, injectable, implantable), intrauterine device (IUD) or intrauterine hormone-releasing system (IUS), bilateral tubal occlusion, a vasectomized partner, or sexual abstinence if in the preferred and usual lifestyle of the patient. These same criteria are applicable to partners of patients involved in this clinical study if that partner is of childbearing potential. Postmenopausal females (no menses for 12 months without an alternative medical cause) and surgically sterilized females are exempt from this criterion.

*Note: In the context of this guidance, sexual abstinence is considered a highly effective method only if defined as refraining from heterosexual intercourse during the entire period of risk associated with the study treatments. The reliability of sexual abstinence needs to be evaluated in relation to the duration of the clinical study and the preferred and usual lifestyle of the subject.

5.1.2 Exclusion Criteria

Patients who meet any of the following criteria will be excluded from study entry:

1. Patients with primary central nervous system (CNS) lymphoma;
2. Any of the following laboratory abnormalities:
 - Absolute neutrophil count $<1.0 \times 10^9/L$
 - Hemoglobin $< 80 \text{ g/L}$
 - Platelets $<50 \times 10^9/L$

NOTE: In the dose expansion stage, patients with cell counts below the thresholds listed above may be considered eligible if, in the investigator's opinion, the reason is bone marrow infiltration. The investigator will discuss the eligibility of such patients with the sponsor, and only upon approval by the sponsor will a patient with cell counts below the thresholds be enrolled in the study.

NOTE: In the dose expansion stage, patients with \leq Grade 2 neutropenia per CTCAE version 5.0 and/or thrombocytopenia and with confirmed bone marrow infiltration are eligible.

3. Inadequate organ function, defined by the following:
 - Total bilirubin >1.5 times the upper limit of normal (\times ULN), with the following exception:
 - Patients with known Gilbert's disease who have serum total and direct bilirubin level $\leq 2.5 \times$ ULN and normal AST and ALT can be enrolled.

- AST or ALT $> 2.5 \times$ ULN, with the following exception:
 - In the dose expansion stage, patients with documented disease infiltration of the liver may have AST and ALT levels $\leq 5 \times$ ULN.
 - Estimated creatinine clearance (CrCl) per Cockcroft-Gault
 - Dose escalation stage of trial (Stage 1) – CrCl < 40 mL/min
 - Dose expansion stage of trial (Stage 2) – CrCl < 30 mL/min
4. International normalized ratio (INR) $> 1.5 \times$ ULN, activated partial thromboplastin time (aPTT) $> 1.5 \times$ ULN;
- Patients requiring anticoagulation therapy but with a stable INR within the recommended range according to the local guideline are eligible.
- NOTE: Patients may be considered for this study if kidney function is impaired but this impairment is believed to be a result of the patient's underlying disease. The investigator will discuss the eligibility of such patients with the sponsor, and only upon approval by the sponsor will a patient with impaired kidney function due to underlying disease be enrolled in the study.
5. Serum amylase or lipase $> ULN$ at screening or known medical history of serum amylase or lipase $> ULN$;
- NOTE: Patients with known medical history of serum amylase or lipase $> ULN$ are eligible in the dose expansion stage.
6. Patients with presence of second primary malignant tumors within the last 2 years, with the exception of:
- Basal cell carcinoma of the skin
 - Squamous cell carcinoma of the skin
 - Carcinoma in situ of the cervix
 - Carcinoma in situ of the breast
7. Clinically significant history of liver disease, including cirrhosis, current alcohol abuse, or current known active infection with human immunodeficiency virus (HIV), hepatitis B virus (HBV), hepatitis C virus (HCV), or cytomegalovirus (CMV); Active infection is defined as one requiring treatment with antiviral therapy, presence of positive test results for hepatitis B (hepatitis B surface antigen and/or total hepatitis B core antibody), or CMV or HCV antibody
- Patients who are positive for hepatitis B core antibody are eligible only if test results are also positive for hepatitis B surface antibody and polymerase chain reaction (PCR) is negative for HBV deoxyribonucleic acid (DNA). These patients will require HBV DNA PCR monitoring, as per local standards
 - Patients who are positive for CMV or HCV serology are eligible only if testing for CMV DNA or HCV RNA is negative.
8. Any anticancer therapy, including chemotherapy, hormonal therapy, biologic therapy, vaccine, or radiotherapy within 3 weeks prior to initiation of study treatment;
9. Any granulocyte colony-stimulating factor treatment/blood transfusion within 7 days before the screening hematology test;

10. Any steroid therapy or approved targeted small molecule agents for anti-neoplastic intent within 7 days or approximately 5 half-lives, whichever is longer, prior to initiation of study treatment;
11. Prior use of any drug that is a strong inducer of CYP3A4 or strong inhibitor of CYP3A4 within 2 weeks prior to initiation of study treatment (3 weeks for St John's Wort) (refer to [Appendix 8](#));
12. Prior autologous transplant within 6 months prior to initiation of study treatment;
13. Prior allogeneic stem cell transplant within 6 months prior to initiation of study treatment or with any evidence of active graft versus host disease or requirement for immunosuppressants within 21 days prior to initiation of study treatment;
14. Clinically significant active infection (e.g., pneumonia) or interstitial lung diseases (including drug induced pneumonitis);
15. Major surgical procedure within 4 weeks prior to initiation of study treatment;
16. Treatment within a clinical study of an investigational agent or using an investigational device within 30 days prior to initiation of the current study treatment;
17. Adverse events from prior anti-neoplastic therapy that have not resolved to Grade \leq 1, except for alopecia;
18. Pregnant (positive urine or serum beta human chorionic gonadotropin [β -HCG] test) or lactating women;
19. New York Heart Association (NYHA) Class II or greater congestive heart failure;
20. Congenital long QT syndrome or corrected QT interval (QTc) $>$ 470 msec;
21. Currently use medication known to cause QT prolongation or torsades de pointes (see full list at [http:// www.crediblemeds.org](http://www.crediblemeds.org));
22. History of myocardial infarction or unstable angina within 6 months prior to initiation of study treatment;
23. History of stroke or transient ischemic attack within 6 months prior to initiation of study treatment;
24. Inability to take oral medication, prior surgical procedures affecting absorption, or active peptic ulcer disease;
25. History of inflammatory bowel disease (e.g., Crohn's disease or ulcerative colitis);
26. Patients with ongoing chronic gastrointestinal diseases;
27. Legally protected adults;
28. Any other diseases, metabolic dysfunction, physical examination finding, or clinical laboratory finding that, in the investigator's opinion, gives reasonable suspicion of a disease or condition that contraindicates the use of an investigational drug or that may affect the interpretation of the results or renders the patient at high risk of treatment complications.

5.2 Study Treatment

5.2.1 Formulation, Packaging, and Handling

HMPL-689 capsules of 2 strengths (2.5 mg and 10 mg) will be used in this clinical study. The capsules are packaged in white high-density polyethylene (HDPE) bottles. The capsules are composed of widely used pharmaceutical excipients (United States pharmacopeia [USP] grade or equivalent) and HMPL-689 drug substance. The drug will be stored at temperatures between 10°C and 30°C and should remain in its bottle until administration in order to avoid unprotected exposure to sunlight. For further details, please refer to HMPL-689 IB and the pharmacy manual.

5.2.2 Drug Labeling

The contents of the label will be in accordance with all applicable regulatory requirements.

5.2.3 Drug Accountability

All IP required for this study will be provided by HUTCHMED Limited or contracted Contract Research Organization (CRO). The recipient will acknowledge receipt of the drug by completing and keeping the appropriate documentation form indicating shipment content and condition. Damaged supplies will be replaced.

Accurate records of all IP received at, dispensed from, returned to and disposed by the study site should be recorded by using the Drug Inventory Log.

Investigational product will be disposed of at the study site according to the study site's institutional standard operating procedure, and the method of destruction must be documented.

5.2.4 Dosage, Administration, and Compliance

The proposed dosage of HMPL-689 is specified in [Table 2](#). Investigational product should be taken at approximately the same times each day. Ideally, doses in the QD cohorts should be taken at 24-hour intervals with ± 4 -hour window. HMPL-689 can be taken with or without food with approximately 8 ounces (240 mL) of water. The administration time should be accurately recorded in the patient diary.

In the study, patients will not be allowed to make up missed doses; patients will resume dosing at their next scheduled dose.

Guidelines for dosage modification and treatment interruption or discontinuation are provided in [Section 5.3](#).

Any overdose ([Section 6.3.1.6](#)) or incorrect administration of IP should be noted on the patient's source documentation and Case Report Form (CRF). Adverse events associated with an overdose or incorrect administration of IP should also be recorded on the patient's source documentation and Adverse Events page on the CRF ([Section 6.3.1.6](#)) and treated according to [Section 5.5](#).

CCI

CCI

5.2.6 Post-trial Access to HMPL-689

Currently, the sponsor does not have any scheduled plans to provide HMPL-689 or any other study interventions after the end of the study or for any patient who has discontinued or withdrawn from the study. The sponsor will evaluate whether to continue providing HMPL-689 after the study is over.

In the event that the sponsor deems post-trial access to HMPL-689 to be appropriate, the sponsor may offer post-trial access to the IP (HMPL-689) free of charge to eligible patients as outlined below.

A patient will be eligible to receive IP after the end of the study if all of the following conditions are met:

- The patient has relapsed/refractory/resistant lymphoma that requires continued IP treatment for his or her well-being.
- There are no appropriate alternative treatments available to the patient.
- The patient and his or her doctor comply with and satisfy any legal or regulatory requirements that apply to them.

A patient will not be eligible to receive IP after the end of the study if any of the following conditions are met:

- The IP is commercially marketed in the patient's country and is reasonably accessible to the patient (e.g., is accommodated by the patient's insurance or would not otherwise create a financial hardship for the patient).
- The sponsor has discontinued development of the IP or data suggest that the IP is not effective for lymphoma.
- The sponsor has reasonable safety concerns regarding the IP as treatment for lymphoma.
- Provision of IP is not permitted under the laws and regulations of the patient's country.

5.3 Method of Treatment Assignment

Patients will be assigned to dose levels sequentially at dose escalation stage. However, in the dose expansion stage, patients will be allocated based on disease subtype.

5.4 Dose Delays and Modification

Refer to Section 6.8 for recommendations on diagnosis and management of potential toxicities associated with HMPL-689 and/or noted with other PI3K δ inhibitors. The recommendations provided in Section 6.8 should be evaluated in conjunction with the local clinical standard of care, and overall management plan should be based on the investigator's best clinical judgment.

5.4.1 During Dose Limiting Toxicities Assessment Window

If a patient experiences a DLT, dosing of HMPL-689 will be interrupted and supportive therapy administered as required in accordance with local practice/guidelines. Refer to Section 6.8 for toxicity management recommendations.

Patients who experience a DLT may resume dosing at the same or previous lower dose level at the discretion of the treating physician given that the toxicity is resolved or improved to the baseline level. If a patient experiences an intolerable toxicity at the reduced dose level, he/she will be discontinued from the study treatment. Patient cannot be dose-reduced by more than 2 dose levels. Once reduced, the dose cannot be re-escalated.

No dose reduction in patients without DLT is permitted in the DLT assessment window without the sponsor's approval.

5.4.2 After Dose Limiting Toxicities Assessment Window of Stage 1 or at Stage 2

After DLT assessment window of Stage 1 or at Stage 2, the dose of HMPL-689 may be interrupted if any of the following is observed:

- Any grade pulmonary toxicity
- Any grade diarrhea/colitis
- Grade 3 or 4 hematologic toxicity
- Grade 3 or 4 non-hematologic toxicity (except for alopecia and skin eruption, nausea, vomiting, diarrhea or constipation if well-controlled by systemic or topical medication)

Refer to Section 6.8 for detailed toxicity management recommendations for potential class-related toxicities and dose modification of HMPL-689.

For all other toxicities, treatment with HMPL-689 should be withheld until the toxicity resolves to CTCAE Grade ≤ 2 . Dosing may then be resumed at either the same dose level or the previously evaluated lower dose level if the toxicity is improved to CTCAE Grade ≤ 2 within 2 weeks, per investigator's discretion. If treatment is resumed at the same dose, and the patient experiences the same toxicity of Grade 3 or 4, the dose should be reduced following resolution of the event. If the patient continues to experience intolerable toxicity, a second dose reduction to a previously evaluated lower dose is permitted.

In all cases, every patient is allowed to reduce HMPL-689 dose only twice. If a patient continues to experience intolerable toxicity after 2 dose reductions, or if dosing with HMPL-689 is interrupted for >14 consecutive days due to toxicity (except for those with additional guidance provided in Section 6.8), treatment should be discontinued, unless otherwise agreed by the investigator and the sponsor.

Intra-patient dose escalation to a higher dose level may be permitted by the sponsor provided that the dose level to be escalated has already been cleared at the time of dose increase being proposed.

5.5 Treatment of Overdose

For this study, any dose of study drug greater than the intended daily dose will be considered an overdose (Sections 5.2.4). Procedures for recording overdose events are available in Section 6.3.1.6.

No specific information is available on treatment of overdose of HMPL-689. Nevertheless, in the event of overdose, further HMPL-689 administration should be withheld and subject should be observed closely for clinical features of toxicities. Appropriate supportive treatments should also be provided if clinically indicated.

5.6 Concomitant Therapy and Food

5.6.1 Permitted Therapy

Concomitant therapy includes any medication (e.g., prescription drugs, over-the-counter drugs or homeopathic remedies, nutritional supplements) used by a patient from 7 days prior to the screening visit to 30 days after the end of treatment or early termination. All such medications should be reported to the investigator and recorded on the Concomitant Medications page of CRF.

Beyond Cycle 1 of Stage 1 or in Stage 2, patients may receive treatment with corticosteroids (at dosages equivalent to prednisone ≤ 20 mg/day) and/or bisphosphonates for the treatment of bone metastases. Patients may also receive palliative radiotherapy for painful bony metastases. If a patient needs to undergo palliative local radiotherapy to relieve symptoms (such as local radiotherapy to relieve cancer bone pain), the patient may resume administration of the study IP 7 days after the local radiotherapy is over, but should meet the following criteria:

- The patient's radiotherapy-related toxicity has recovered to <Grade 2; and
- The tumor has not progressed.

5.6.2 Prohibited Therapy and Food, and Concomitant Medications Requiring Caution in Use

Patients receiving strong inducers of CYP3A4 or strong inhibitors of CYP3A4 within 2 weeks before the first dose of study treatment (3 weeks for St John's Wort) are excluded from the study. Concomitant use of drugs that are known to be strong inducers of CYP3A4 or strong inhibitors of CYP3A4 during the trial should be avoided as far as possible unless considered essential by the investigator, in which case patients must be monitored closely for potentially reduced efficacy or increased toxicity due to drug-drug interactions.

Drugs that are known to be affected by P-gp should be used with caution.

[Appendix 8](#) provides lists of drugs prohibited and those that should be used with caution. These lists are not intended to be exhaustive, please refer to full prescribing information for all drugs prior to concomitant use with HMPL-689.

Other anticancer agents, investigational agents, and radiotherapy (not for painful bony lesion) should not be given while the patient is during the study.

Corticosteroids are prohibited from 7 days before the date of hematologic screening test to the end of DLT assessment window of Cycle 1 of Stage 1.

Granulocyte colony stimulating factors should not be used prophylactically during the DLT assessment window. Use of prophylactic colony stimulating factors may be considered after Cycle 1 following discussion with the sponsor.

No grapefruit or grapefruit juice or recreational drugs will be allowed during the study.

HMPL-689 shows pH-dependent solubility (i.e., solubility at pH 4.5-6.8 < solubility at pH 1-2) and may be less well absorbed as gastrointestinal pH increases. Patients should avoid using proton pump inhibitors (e.g., esomeprazole, lansoprazole, pantoprazole) during the study. If concomitant use of an acid-reducing agent is unavoidable, H₂-antagonist (e.g., famotidine, ranitidine, nizatidine) may be used but should be administered approximately 10 hours before or 2 hours after HMPL-689 dosing. Antacid may be used, but the antacid dose should be administered at least 2 hours before or 2 hours after HMPL-689 dosing.

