4.1.1.3 Dose Limiting Toxicity Assessment Window

For all patients in Stage 1, DLTs will be assessed during a DLT assessment window of 28 days (i.e., from Cycle 1, Day 1 [the day of first administration of treatment] through Cycle 1, Day 28).

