6.8 HMPL-689 Dose Modification and Toxicity Management Algorithm for Clinical Trials

This section provides guidance to the investigators for the differential diagnosis and management of the important potential class toxicities noted on HMPL-689 trials and/or those associated with other PI3K δ inhibitors. This constitutes general recommendations to investigators involved in HMPL-689 studies and should be supplemented with any additional protocol-specific guidance. In case of questions, prompt discussions with the sponsor's clinical representative are recommended. Please see [Table 6](#), [Table 7](#), [Table 8](#), [Table 9](#), [Table 10](#), [Table 11](#), and [Table 12](#) for the dose modification and toxicity management recommendations for pulmonary AEs (including pneumonia/pneumonitis), diarrhea/colitis, hepatic AEs, infection, neutropenia, thrombocytopenia, and rash and cutaneous skin reactions, respectively.

As a general principle, the recommendations are as follows:

- Differential diagnosis for any adverse event should be diligently evaluated according to standard medical practices.
- Recommendations provided here should be evaluated in conjunction with the local clinical standard of care, and overall management plan should be based on the investigator's best clinical judgment.
- Consultation with specialty medical care is recommended as appropriate and especially prior to any invasive diagnostic or therapeutic procedures.

Table 6 Dose Modification/Toxicity Management Recommendations for Pulmonary Adverse Events Including Pneumonia/Pneumonitis

Adverse Reaction CTCAE V5.0 Grade/Severity	Recommended Management	Recommended Dosing Modification	Recommended Follow-up

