	
 • If determined as non-infectious (i.e., with immune component), promptly consider systemic steroid treatment 
 ○ Administer methylprednisolone IV 1 to 2 mg/kg/day or equivalent oral corticosteroid dose 		
corticosteroids (e.g., prednisone) during the steroid taper.
 
 • If etiology unclear and resolves without a need for systemic steroid treatment, then study drug treatment may be restarted at a reduced dose based on investigator’s clinical judgment • Monitor closely on restarting treatment; if symptoms recur (at either same or reduced dose), then permanently discontinue the study drug

Adverse Reaction CTCAE V5.0 Grade/Severity	Recommended Management	Recommended Dosing Modification	Recommended Follow-up

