
Grade 3 or Grade 4
 
(Severe or life-threatening symptoms, new or worsening hypoxia)
	
 • Hospitalize for further management • Request pulmonary and/or infectious disease consult • Evaluate differential diagnosis and causality (as described above) • Prompt treatment with antibiotic, antifungal, or appropriate treatment as per standard guidelines • Prompt treatment with systemic steroids, if considered non-infectious or for suspected immune-related events 
 ○ Administer 1 to 2 mg/kg/day IV methylprednisolone or equivalent • Consider bronchoscopy and lung biopsy if clinically indicated 	
Withhold study drug
	
 • Continue close follow-up and re-imaging and increase steroid dose, as needed • If considered infectious etiology: 
 ○ If resolved to baseline within 28 days, resume study drug at a reduced dose ○ If not resolved within 28 days, permanently discontinue study drug. ○ If worsens or recurs on restarting treatment, permanently discontinue study drug • If considered immune-related or non-infectious etiology: 
 ○ Permanently discontinue study drug and treat promptly with steroids (including gradual tapering) 
 – If not improving after 48 hours or worsening, consider additional immunosuppression – After sustained clinical improvement is observed, gradually taper steroids (e.g., by 5 to 10 mg/week over 4 to 6 weeks) per institutional standards – Patients can be switched to an equivalent/appropriate dose of oral corticosteroids (e.g., prednisone) during the steroid taper

BAL = bronchoalveolar lavage; CMV = cytomegalovirus; COVID-19 = coronavirus 2019; CTCAE = Common Terminology Criteria for Adverse Events; DNA = deoxyribonucleic acid; HRCT = high-resolution computed tomography; ILD = interstitial lung disease; IV = intravenous; KL-6 = Krebs von den Lungen-6; PFT = pulmonary function test; PJP = *Pneumocystis jiroveci* fungus; RT-PCR = real-time polymerase chain reaction; SP-D = serum surfactant protein D; SpO2 = oxygen saturation.

Table 7 Dose Modification/Toxicity Management Recommendations for Diarrhea/Colitis

Adverse Reaction CTCAE V5.0 Grade/Severity	Recommended Management	Recommended Dosing Modification	Recommended Follow-up

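### Protocol 5.6.2 bans corticosteroids through the Stage 1 DLT window with no toxicity exception, while 5.4.1 and 6.8 lead to prompt steroids in that window; after Cycle 1 the steroid rule is ambiguous

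*Protocol*

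**What the plan says.** **Protocol 5.6.2:** "Corticosteroids are prohibited from 7 days before the date of hematologic screening test to the end of DLT assessment window". The window meant is Cycle 1 of Stage 1. Under Protocol 4.1.1.3, "DLTs will be assessed during a DLT assessment window of 28 days", starting on Cycle 1 Day 1.

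**Protocol 5.6.1**, for Stage 2 and for Stage 1 patients past their first cycle: "patients may receive treatment with corticosteroids (at dosages equivalent to prednisone ≤ 20 mg/day) and/or bisphosphonates for the treatment of bone metastases". This is the only permission for corticosteroids in Section 5.6.

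**Protocol 5.4.1**, on DLTs inside the window: dosing is interrupted, supportive treatment is given according to local practice, and the reader is referred to Section 6.8.

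**Protocol 6.8, Table 6:**
- Grade 3/4 pulmonary events judged non-infectious or suspected immune-related get prompt systemic steroids: "Administer 1 to 2 mg/kg/day IV methylprednisolone or equivalent".
- For Grade 2 non-infectious events the table advises promptly considering systemic steroids, then says: "Administer methylprednisolone IV 1 to 2 mg/kg/day or equivalent oral corticosteroid dose".

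**Protocol 6.8, Table 7:**
- Grade 4 diarrhea or colitis: prompt systemic steroids at the same dose and/or empiric antibiotics.
- Non-infectious Grade 3 diarrhea or Grade 2/3 colitis: prompt enteric-acting or systemic steroids.

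**Protocol 6.8, Tables 8 and 12:** for hepatic events and Grade 3 rash, steroids are only to be considered. Table 8 gives no dose.

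**Status of 6.8:** it describes itself as general recommendations that "should be supplemented with any additional protocol-specific guidance".

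**The concern.** A Stage 1 patient with severe non-infectious pneumonitis or colitis in Cycle 1 falls under two instructions at once: a flat ban on corticosteroids, and a management table that calls for them promptly. A site that treats Section 5.6 as the protocol-specific rule could hold back. A site that opens Section 6.8 would treat and could have the steroid recorded as a prohibited medication. Neither reading is unreasonable on the text.

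For the patient, this concerns the class toxicities that Section 6.8 was written to manage. For the analysis, SAP 9.2 tabulates major protocol deviations by category. SAP 17.2 summarizes duration and outcome of adverse events of special interest, whose categories include interstitial lung disease, noninfectious diarrhea, abnormal hepatic function and severe cutaneous reactions. Both outputs could partly reflect which section a site followed. The documents give no data from which to size that effect.

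**Working it through.** The plan has no sample-size or power figure on this point to reproduce. The check is a comparison of texts plus one dose comparison.

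**1. Do the two rules meet in the same patient at the same time?** Yes. Protocol 4.1.1.2 makes non-hematologic events of Grade 3 or higher DLTs, apart from controllable nausea or vomiting and events attributed to the malignancy or another cause. A Grade 3/4 pulmonary event, or Grade 3/4 diarrhea or colitis, on Days 1 to 28 of Stage 1 would therefore normally be a DLT. Section 5.4.1 sends that patient to Section 6.8 while the 5.6.2 ban is still running. Grade 2 colitis is not a DLT by grade alone, but Section 5.4 refers to 6.8 for toxicity management in general.

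**2. Can a toxicity exception be read into 5.6.2?** Not safely. Two neighboring rules in that section are qualified. Strong CYP3A4 inducers and inhibitors may be used if the investigator finds them essential, and growth factors are barred in the window only as prophylaxis. The corticosteroid sentence has no such qualifier and names no dose, route or purpose. The enteric-acting option in Table 7 is therefore not clearly outside it.

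**3. Does anything set precedence?** Not in the supplied text. Section 5.6 does not mention 6.8, and 6.8 does not mention the limits in 5.6.

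**4. How firmly does 6.8 call for steroids?**

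| Entry in 6.8 | Strength | Systemic dose (methylprednisolone) |
|---|---|---|
| Table 6, Grade 3/4, non-infectious | Prompt treatment | 1 to 2 mg/kg/day |
| Table 6, Grade 2, non-infectious | Consider promptly, then administer | 1 to 2 mg/kg/day |
| Table 7, Grade 4 | Prompt, and/or antibiotics | 1 to 2 mg/kg/day |
| Table 7, Grade 3 diarrhea or Grade 2/3 colitis, non-infectious | Prompt start; enteric-acting alternative | 1 to 2 mg/kg/day |
| Table 8, AST/ALT elevation | Consider | None given |
| Table 12, Grade 3 rash | Consider | 0.5 to 1 mg/kg/day |

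**5. Does the 5.6.1 permission cover the 6.8 doses?** Inputs: 1 to 2 mg/kg/day (Tables 6 and 7) and 20 mg/day (5.6.1). Body weight and the methylprednisolone-to-prednisone conversion are not in the documents. Both are assumed: 50, 70 and 100 kg, at 1:1.

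Ratio = (mg/kg/day × weight × conversion) / 20

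- 50 kg: 50 to 100 mg/day; 50/20 = 2.5 to 100/20 = 5 times
- 70 kg: 70 to 140 mg/day; 70/20 = 3.5 to 140/20 = 7 times
- 100 kg: 100 to 200 mg/day; 100/20 = 5 to 200/20 = 10 times

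With an assumed conversion of 1.25 instead, the top of the range is 200 × 1.25 / 20 = 12.5 times. At 1:1, 1 mg/kg/day stays within 20 mg/day only at 20/1 = 20 kg or less, which is not a plausible adult weight. The Table 12 rash dose runs from 0.5 × 50 = 25 mg/day to 1 × 100 = 100 mg/day, or 1.25 to 5 times. The permission does not cover these doses. Inside the Stage 1 window the permitted amount is zero.

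**The case against.** **A stronger reading is tempting:** that 5.6.1 caps steroids at 20 mg/day for all later treatment, so a site must always break one section to follow the other. The text does not support this. Section 5.6.1 grants a permission and does not say that nothing else is allowed. Its reference to bone metastases may govern the corticosteroids as well as the bisphosphonates, in which case the figure does not concern toxicity treatment at all. Section 5.6.2 contains no steroid ban after the window. A Stage 2 site following 6.8 goes beyond the stated permission but breaks no express prohibition.

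**6.8 only recommends.** It defers to local standard of care and clinical judgment, several entries only advise considering steroids, and 5.4.1 allows supportive treatment under local practice. This stands in part: no site is strictly compelled to give steroids. But the firmest entries are worded as instructions, and calling 6.8 general makes it easier to let the flat ban in 5.6.2 prevail.

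**Study drug is stopped permanently when systemic steroids are needed for non-infectious lung or bowel events.** True, and it limits the practical effect. However, 5.6.1 counts concomitant therapy until 30 days after treatment ends, and nothing says the ban lapses on discontinuation. Study drug may also resume after Grade 3 rash or Grade 3 AST/ALT elevation, and it continues during Grade 1/2 AST/ALT elevation.

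**Enrollment is halted.** This stands. Under Amendment 5 no new patient can enter the Stage 1 window, so that conflict is largely a matter of how past steroid use was classified.

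**No document classes toxicity-directed steroids as a deviation, and Appendix 8 is not in the supplied text.** Both stand. Miscounted deviations are a possibility, not a demonstrated fact, and a qualification in Appendix 8 cannot be excluded.

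**Conclusion.** The contradiction holds for the Stage 1 DLT window: 5.6.2 prohibits without exception what 5.4.1, through Tables 6 and 7 of 6.8, calls for in the same patient and period. It is clearest for Grade 3/4 non-infectious pulmonary events. It is softer for the bowel entries, which offer antibiotics or an enteric-acting alternative, and weakest for Tables 8 and 12.

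After Cycle 1 and in Stage 2 there is an ambiguity only. The single permission in 5.6.1 falls short of the Table 6 and 7 doses by a factor of about 2.5 to 10, given the assumed 50 to 100 kg and 1:1 conversion, and the text does not say whether that permission was meant to apply to treating toxicity. This part still matters to patients who remain on drug under Amendment 5.

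The point is a should-fix clarification. It rests on the supplied text, without Appendix 8, and takes no view on which clinical rule is right.

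**What to change.** - Reconcile 5.6.1 and 5.6.2 with 5.4.1 and 6.8.
- State in 5.6 which section governs corticosteroids given to treat an adverse event, separately for the Stage 1 DLT window and for later treatment. Say whether the 5.6.1 figure relates only to bone metastases, and check Appendix 8 for consistency.
- Classify protocol deviations to match, and apply the same classification retrospectively to Stage 1 before the SAP 9.2 table is produced.

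The content of the clinical rule is for the sponsor's clinicians and the SRC.

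Cost: a protocol clarification letter or minor amendment and a review of Stage 1 steroid records already held. No new patients or data collection are needed.
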